9.1.1 Primary end-points

- Safety: Risk of intracranial hemorrhage (intracerebral hemorrhage, subarachnoid hemorrhage, subdural and epidural hematoma), among NVAf patients in the UK associated with appropriately and inappropriately receiving standard and reduced dose in new-users of apixaban, rivaroxaban, or warfarin for stroke prevention.
- Effectiveness: Risk of ischemic events (ischaemic stroke /systemic embolism, myocardial infarction), among NVAf patients in the UK associated with appropriately and inappropriately receiving standard and reduced dose in new-users apixaban, rivaroxaban, or warfarin for stroke prevention.

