8.1 Primary objective

- To compare the safety of rivaroxaban (20mg and 15mg; OD) and apixaban (5mg and 2.5mg; BID) vs warfarin in patients appropriately and inappropriately receiving standard and reduced doses of each NOAC in accordance with the label for SPAF.
 - Intracranial hemorrhage (intracerebral hemorrhage, subarachnoid hemorrhage, subdural and epidural hematoma)
 - Hemorrhagic stroke (intracerebral hemorrhage, subarachnoid hemorrhage)
- To compare the effectiveness of rivaroxaban (20mg and 15mg; OD) and apixaban (5mg and 2.5mg; BID) vs warfarin in patients appropriately and inappropriately receiving standard and reduced dose in accordance with the label for SPAF.
 - Ischaemic Stroke and Systemic Embolism
 - Myocardial Infarction

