9.3.2 Outcomes definition

The outcomes include

- Intracranial hemorrhage (intracerebral hemorrhage, subarachnoid hemorrhage, subdural and epidural hematoma)
- Ischemic event (Ischaemic Stroke /Systemic Embolism),
- Myocardial Infarction
- All cause-mortality

See section [Annex 3: Additional information](#) for corresponding codes.

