9.5 Study size

Study 19330 (unpublished data) conducted in UK identified 8,629 initiators of apixaban and 12,353 initiators of rivaroxaban among patients with NVAf from 2011 through 2016 within the THIN database. A study conducted in UK between 1 December 2012 and 31 October 2014 using CPRD, reported 10,218 naïve users of warfarin (Johnson et al. 2016). With an additional year up to 2017, the expected numbers of Rivaroxaban, Apixaban and Warfarin users will be greater than numbers reported above. Thus, assuming the study will include at least 10,000 initiators of each study drug and annual rates of intracranial hemorrhage, ischemic stroke, and all-cause mortality of 1%, 2%, and 4%, we expect the study to identify at least a total of 900, 1800, and 3600 events respectively. In case only 50% of initiators continue drug use at index date (i.e. current users at index date), we should be able to detect, with a statistical power greater than 80%, odds ratios of 1.5 associated to current use of each study drugs for intracranial haemorrhage, odds ratios of 1.3 for ischemic stroke, and odds ratios of 1.2 for all-cause mortality.

Regarding the daily dose analyses, power calculation will depend largely on the percentage of individuals we found in each daily dose category. For instance in, if we assume that 30% of current users of apixaban will use a reduced dose (2.5mg Bid), half of them appropriately, for the comparison between “appropriate” and “inappropriate” reduced dose of apixaban we would be able to detect odds ratios of 3.5 when exploring intracranial hemorrhage, odds ratios of 2.4 for ischemic stroke, or odds ratios 1.8 for all-cause death. On the other hand for the comparison between “inappropriate” reduced dose of apixaban versus warfarin current use, if the assumptions described above hold, we should be able to detect with a power of at least 80% odds ratios of 2.3, 1.8, and 1.6 for ICH, IS, and all-cause mortality respectively. Note that all these calculations have assumed a two-sided type I error of 5%.

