9.7 Data Analysis

We will first describe the three cohorts according baseline characteristics, use of medications, comorbidities and healthcare utilization services (see variables in section 9.3). This analysis will be based on descriptive statistics: frequencies and percentages will be calculated to the variables of interests, continuous and count variables will be described using mean (\pm standard deviation), proportions, median (quartiles) and minimum and maximum values. 95% confidence intervals will be computed for descriptive variables.

Two independent follow-ups will be performed, one for each analysis. **Safety and effectiveness:** In this follow-up members of all three study cohorts will be followed from the day after start date up until the earliest of: a) first occurrence of Intracranial hemorrhage (intracerebral hemorrhage, subarachnoid hemorrhage, subdural and epidural hematoma), b) an ischemic event (Ischaemic Stroke /Systemic Embolism), c) Myocardial Infarction, d) death, and e) end of study period. **All-cause Mortality:** the follow-up of members of all three study cohorts will be followed from the day after start date up until the earliest of: a) date of death, and b) end of study period. The end of study period is defined as end of last data collection in each practice.

We will then analyze safety, effectiveness, and all-cause mortality associated to use of the study drugs in three independent nested-case control analyses. These three analyses will include all cases identified in each follow-up (respectively: intracranial hemorrhage events, ischemic events, and deaths) and an analysis-specific group of controls. These control groups will comprise a random sample of members of all three cohorts, frequency-matched by age, sex and calendar year to each set of cases ([Walker 1991](#)). Briefly, each cohort member is assigned a random date within the study period. We will consider “eligible controls” all those individuals who are being followed at the time of the random date (e.g. random date included between their start of follow-up and end of follow-up). This process (similar to incidence density sampling) ensures that the likelihood of being selected as control is proportional to the amount of person-time contributed by each patient: as an example a person who contributes all the time included between beginning of study period and end of study period has a 100% likelihood of being an eligible control. Then we will sample “eligible

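### The protocol does not settle whether MI belongs to the primary effectiveness case set, and neither MI nor haemorrhagic stroke has its own named analysis or sizing

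*Protocol*

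**What the plan says.** - **Protocol 8.1 (objectives).** Four bullets. Under safety: ICH and, separately, "Hemorrhagic stroke (intracerebral hemorrhage, subarachnoid hemorrhage"). Under effectiveness: ischaemic stroke with SE and, separately, MI.
- **Protocol 9.1.1 (end-points).** Two end-points. Safety is ICH. Effectiveness reads "Effectiveness: Risk of ischemic events (ischaemic stroke /systemic embolism, myocardial infarction), among NVAf patients in the UK". Haemorrhagic stroke is not mentioned.
- **Protocol 9.3.2 (outcome definitions).** One bullet is "Ischemic event (Ischaemic Stroke /Systemic Embolism"); MI is a bullet of its own. Haemorrhagic stroke is not listed.
- **Protocol 9.7 (follow-up; also the Abstract).** Follow-up ends at the first of ICH, an ischaemic event (glossed as stroke/SE), MI, death or end of study. MI again stands apart.
- **Protocol 9.7 (case sets).** There are three nested case-control analyses, with cases given as "respectively: intracranial hemorrhage events, ischemic events, and deaths", each with its own frequency-matched controls. The section later says that the listed comparisons apply to every outcome, without saying which list of outcomes is meant.
- **Annex 3, Table S9.** The table of codes for ischaemic events in the effectiveness analysis opens with MI codes, then gives stroke codes and SE codes.
- **Protocol 9.5 (sizing).** It is built on "annual rates of intracranial hemorrhage, ischemic stroke, and all-cause mortality of 1%, 2%, and 4" percent. No rate, event count or detectable odds ratio is given for MI or haemorrhagic stroke.

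**The concern.** The primary effectiveness odds ratio measures whatever the ischaemic-event case set contains, and the protocol gives that set two different contents. The study hypothesis (section 7) is that inappropriate dose reduction raises stroke and SE. MI is included for another reason: section 7 cites evidence that rivaroxaban may lower it. If MI is pooled, the odds ratio no longer isolates the hypothesis. If MI is kept out, an outcome that 8.1 calls primary has no case set. Neither reading delivers 8.1. The same loose term carries over to the description of drug use after an event: the objective in 8.2 refers to ischaemic stroke, while 9.3.1 and 9.7 refer to ischaemic events.

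**Working it through.** **1. The two readings side by side**

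| Place | MI inside ischaemic events? | Haemorrhagic stroke named? |
|---|---|---|
| 8.1 objectives | Separate outcome | Yes, separate outcome |
| 9.1.1 end-points | Inside | No |
| 9.3.2 outcomes | Outside | No |
| 9.7 and Abstract, follow-up rule | Outside | No |
| 9.7 case sets | Not stated | No |
| Annex 3 code lists | Inside (Table S9) | No list of its own; subarachnoid and intracerebral codes sit in Table S8 |
| 9.5 sizing | Ischaemic stroke only | No |

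Under 9.1.1 and Table S9, MI cases enter the effectiveness case set and the separate MI objective has no set. Under 9.3.2 and the follow-up rule, MI ends follow-up and falls outside all three named sets.

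**2. Reproducing the sizing in 9.5**

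Inputs from 9.5: at least 10,000 initiators of each of three drugs (30,000 in all), annual rates of 1%, 2% and 4%, 50% still current users at index date, 30% of current apixaban users on the reduced dose and half of those appropriately, two-sided alpha 5%, power 80%.

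Events = 30,000 × rate × mean follow-up. The stated 900, 1800 and 3600 are obtained with 3 years, which is implied but not stated: 30,000 × 3 × 0.01 = 900, and likewise 1800 and 3600.

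Detectable odds ratio: compare exposure proportions in cases and controls within the two exposure groups contrasted, with p1 = p0·OR/(1 − p0 + p0·OR) and the usual two-proportion normal approximation (pooled variance under the null), solved for 80% power. Current users of each drug are 1/6 of the cohort (1/3 × 50%). Inappropriate and appropriate reduced-dose apixaban are 2.5% each (1/6 × 15%). The number of controls per case is not stated; one per case comes close to the stated values:

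| Contrast | Computed, ICH / stroke / death | Stated in 9.5 |
|---|---|---|
| Inappropriate vs appropriate reduced apixaban | 3.54 / 2.37 / 1.82 | 3.5 / 2.4 / 1.8 |
| Inappropriate reduced apixaban vs current warfarin | 2.20 / 1.78 / 1.52 | 2.3 / 1.8 / 1.6 |
| Current use vs non-use | 1.43 / 1.29 / 1.20 | 1.5 / 1.3 / 1.2 |

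The stated figures are thus broadly reproduced. The middle column entries for effectiveness all rest on the 2% ischaemic-stroke rate, that is, on the definition without MI.

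**3. What pooling would do (illustration)**

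The protocol gives no MI rate, so m = 0.5, 1.0 and 1.5% a year is assumed in the reference group. With additive rates, pooled OR = (2 × OR for stroke + m × OR for MI)/(2 + m). Take a stroke OR of 1.8 (the value stated in 9.5 for inappropriate reduced apixaban vs warfarin) and an MI OR of 1.0:

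- m = 0.5: (3.6 + 0.5)/2.5 = 1.64
- m = 1.0: (3.6 + 1.0)/3.0 = 1.53
- m = 1.5: (3.6 + 1.5)/3.5 = 1.46

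The case set would grow from 1800 to 2250, 2700 or 3150, of which MI is 450/2250 = 20%, 900/2700 = 33% or 1350/3150 = 43%.

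**4. Precision if MI and haemorrhagic stroke are analysed separately**

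Same method, one control per case. The share of ICH that is haemorrhagic stroke is also an assumption (40, 60, 80%).

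| Outcome | Events | Drug vs current warfarin | Inappropriate reduced apixaban vs warfarin | Inappropriate vs appropriate |
|---|---|---|---|---|
| MI, 0.5 / 1.0 / 1.5% a year | 450 / 900 / 1350 | 1.93 / 1.59 / 1.46 | 2.93 / 2.20 / 1.93 | 7.1 / 3.5 / 2.7 |
| Haemorrhagic stroke, 40 / 60 / 80% of ICH | 360 / 540 / 720 | 2.10 / 1.82 / 1.68 | 3.28 / 2.70 / 2.39 | 10.3 / 5.6 / 4.2 |

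With four controls per case the last column becomes 4.3 / 2.7 / 2.2 for MI and 5.4 / 3.7 / 3.0 for haemorrhagic stroke.

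**The case against.** A reader might infer that MI and haemorrhagic stroke are not analysed at all. The protocol does not support that. Sections 8.1 and 9.1.1 and Table S9 all place MI under effectiveness, 9.3.2 lists it as an outcome, and 9.7 promises its comparisons for every outcome. Haemorrhagic stroke is by definition a subset of ICH, so every case is in the ICH set, is manually reviewed under 9.3.2.1, and can be separated by its codes in Table S8. What it lacks is a line naming the subset analysis.

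It can also be said that 9.1.1 never uses the word composite: the slash joins stroke to SE, and the comma may simply list MI as a second item. That reading is possible. It does not help, because the term is then used in 9.7 to name a single case set, and the general promise about every outcome creates neither a fourth set nor its matched controls.

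Sizing on stroke alone is not an arithmetic error, and adding MI would only raise the case count. That stands; the point is that the detectable odds ratios do not carry over to a different end-point.

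A statistical analysis plan may add detail. Conflicting definitions of a primary outcome inside the protocol are a different matter from detail left for later.

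**Conclusion.** The contradiction holds on the text alone, without any assumption: the primary effectiveness case set is undetermined, and neither reading gives MI the separate primary analysis that 8.1 calls for. Haemorrhagic stroke lacks an end-point entry, an outcome definition and a named analysis after the objectives. The sizing in 9.5 applies only to ischaemic stroke.

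The dilution from 1.8 to about 1.64–1.46 is an illustration. It rests on assumed MI rates and on dose having no effect on MI, which the protocol does not establish.

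Two stronger conclusions are tempting and are not supported. One is that pooling would tilt effectiveness towards rivaroxaban: the trial odds ratio of 0.8 for MI cited in section 7 has an interval of 0.61 to 1.04, the protocol itself calls the trial results variable, and a real MI reduction would be a genuine effect on a chosen outcome. The other is that the definition will be picked after results are seen; nothing in the protocol shows that. Nor does 8.1 rank stroke/SE above MI, so whether a composite should be secondary is a matter of preference.

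**What to change.** - Use one definition of ischaemic event, ischaemic stroke/SE as already written in 9.3.2 and in the follow-up rule, in 9.1.1, 9.3.2, 9.7 and Table S9.
- In 9.7, name MI as its own case set with its own frequency-matched controls.
- Name haemorrhagic stroke (intracerebral plus subarachnoid) as a subset analysis of the ICH cases, and add it to 9.1.1 and 9.3.2.
- Label the stroke, SE and MI blocks of Table S9 as separate lists.
- In 9.5, give expected events for MI and haemorrhagic stroke with the rates assumed.

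The cost is wording, one further control set and one subset analysis. The cases come from events already coded and due for manual review. Precision for MI and haemorrhagic stroke in the dose-appropriateness comparisons will be limited, and the protocol should say so.

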9.1.2 Secondary end-points

- To evaluate the above mentioned outcomes in the sub-groups of patients with renal impairment and diabetes
- To evaluate all-cause mortality in rivaroxaban and apixaban, as compared to warfarin
- Drug utilisation and patient characterization of rivaroxaban, apixaban and warfarin receiving standard and reduced dose in accordance and not in accordance with the label
- Drug utilisation/prescription behaviour and patient characterization following the first Intracranial haemorrhage or Ischaemic Stroke during the study period

9.2 Setting

9.2.1 Study population

In the UK, nearly all residents are registered in a general medical practice that uses a system of electronic medical records. THIN is a structured, de-identified electronic medical record database in the UK. The population included in THIN is representative of the UK as a whole in terms of age, sex and geographic distribution. THIN now collects data from around 500 practices, covering about 5% of the general population of the UK population (including practices in England, Wales, Scotland, and Northern Ireland). One of the advantages of using THIN for this project is that the knowledge acquired in study 19330, which was recently completed, in a similar population using this database and the possibility to validate the outcomes using manual review of cases and free text comments is key in managing this complex issue of classifying daily-dose of these drugs.

9.2.2 Study time frame

The study period extends from 1st January 2012 up to last available database extraction (at time of writing, December 2017). Rivaroxaban was first marketed in 2008 in the UK, whereas apixaban was introduced in 2011. By choosing this study period we ensure that all three study drugs were available throughout the study.

9.2.3 Selection criteria

Inclusion criteria

- Patients aged ≥ 18 years of age
- NVAf
- New users of Rivaroxaban, Apixaban, Warfarin
- At least one year enrollment with the general practice (GP)
- One year since first health contact recorded in THIN prior to the first prescription of a study drug

Exclusion criteria

- Patients with other recent indications of OAC initiation as described in section 9.1.
- Individuals on more than one OAC on the start date.
- Users of Rivaroxaban apart from 15/20mg daily dose
- Users of Apixaban apart from 5/10mg daily dose

9.2.4 Representativeness

The population included in THIN is representative of the UK as a whole in terms of age, sex and geographic distribution (Blak et al. 2011; Bourke, Dattani, and Robinson 2004). THIN has been extensively validated for use in pharmacoepidemiology (Lewis et al. 2007).

9.3 Variables

9.3.1 Exposure definition

Among the source population resulting from the THIN database, we will ascertain three separate/mutually exclusive cohorts of new-users of rivaroxaban, apixaban and warfarin (index drug) using the date of first prescription (start date) among the three study drugs. Index date= event date in the nested case-control analysis.

This study will apply a new-users (initiators) design (Ray 2003) and then further stratify the new users into naïve and non-naïve. A patient is considered eligible as new user of rivaroxaban, apixaban or warfarin if he or she had a first prescription of the respective drug recorded during the enrolment period and never received one prior for that index OAC. Further, naïve users are individuals with no previous recorded use of any OAC in the database before the start date. Non-naïve patients are those with one or more oral anticoagulant prescriptions other than the index drug recorded before the start date.

The study drug will be further stratified to Current, recent, past and non-use specified in [section 9.3.3](#)

Among cases of intracranial haemorrhage or ischemic events during the study period, use of the study drugs after index date (index date=event date in the nested case-control analysis) will also be ascertained within one year after the index date.

9.3.1.1 Strategy for dose estimation

Apixaban, rivaroxaban and warfarin tablet strength will be derived from the description of the prescribed product. Dosing frequency/posology per day will be derived from the free text recorded instructions for the prescription.

For NOAC, a posology of three or more doses per day (derived from instructions) will not be considered valid. Furthermore, the daily dose of NOAC prescriptions will be assigned by applying the algorithms for deduplication and daily dose assignment as described below.

Deduplication

For any two or more prescriptions for the same NOAC issued on the same day (concurrent), a deduplication will be performed based on the following criteria:

1 – If all concurrent prescriptions are of the same strength, then the one with the greatest quantity (total number) of tablets will be selected.

If not:

2 – If the concurrent prescriptions are for rivaroxaban and one of the concurrent prescriptions is for a tablet strength of 15 mg then this prescription will be selected.

If not:

3 – If there is another prescription of the same NOAC within a window of 30 days after the end of supply of the longest concurrent prescription that matched the strength of one of the original concurrent prescriptions, then this strength will be selected.

If not:

4 –The first prescription as ordered in the database will be selected.

Daily dose assignment

After deduplication, if required, daily dose will be computed with the following rules:

1– If the directly derived posology from text-based dosage instructions have a value of 1 or 2, then the corresponding value of posology of 1 or 2 will be assigned.

If not:

2 – If the NOAC is apixaban, then posology will be assigned to 2.

If not:

3 – If the NOAC is rivaroxaban then the posology is assigned to 1, unless one of the following scenarios are present:

A – When there is concurrent prescription of 15 mg strength and 20 mg strength tablets, then posology will be assigned to 2 for the 15 mg strength. This particular rule applied even when dosage instructions gave valid values of 1 (see rule 1 above).

B – When the rivaroxaban prescription is for 15 mg strength with a quantity of 42 tablets (irrespective of another concurrent rivaroxaban prescription), then posology will be assigned to 2.

Once all these steps are applied, then daily dose will be derived as the simple product of posology value and strength of the selected prescription. Once the daily dose is computed for all NOACs following the rules described above, we will change the daily dose of rivaroxaban assigned to 40 mg to 20 mg when the posology derived from dividing the quantity (number of tablets) by days of time interval between consecutive prescriptions (gap between prescriptions less than 90 days) results in 20 mg daily dose: consequently, correcting the information indentified from the instructions field of the database in this scenario. This amendment to the algorithm was introduced as a result of our exercise in Study 19330, unpublished data. In the case of rivaroxaban, we found that estimating daily dose based on dose instructions (those recorded in the free text field) sometimes results in misclassifying as 40mg daily dose, usage that should be classified as 20mg daily dose according to pill count.

Furthermore estimated daily doses for both start date and index date, will be classified according to whether or not estimated daily dose corresponded to a standard dose. When estimated daily dose at index date, only prior prescriptions will be taken into account. For rivaroxaban a daily dose of 20mg will be considered as “standard dose”. Daily doses of 15mg will be considered a “reduced dose”. For apixaban a daily dose of 10mg will be considered as “standard dose”. Daily doses of 5mg will be considered as “reduced dose”.

For warfarin we will also obtain posology from free text recorded instructions for the prescription using the following criteria:

- 1.- When instructions assign 1, 2 or 3 per day we will consider them as valid and apply that posology.
- 2.- If instructions are missing, not mapped to a value, or mapped to posology other than 1,2, 3 per day, we will assign a value of 1 per day.

Warfarin daily dose will be derived as the simple product of posology value and strength of the selected prescription. In the case of more than one prescription of warfarin on same day (usually different strengths) the daily dose will be the sum of daily doses of all different prescriptions recorded on that day, and the length of supply the largest supply among all different prescriptions recorded on that day.

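### No quantity or strength check for apixaban read as once daily: 5 mg tablets can enter the reduced-dose cell labelled 2.5 mg twice daily

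*Protocol*

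**What the plan says.** All the rules are in Protocol section 9.3.1.1 unless another section is named.

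- **Rule 1, any NOAC.** Where the posologies derived from the dosage text "have a value of 1 or 2, then the corresponding value of posology of 1 or 2 will be assigned".
- **Rule 2, reached only if rule 1 fails.** "If the NOAC is apixaban, then posology will be assigned to 2".
- **Dose.** The "daily dose will be derived as the simple product of posology value and strength of the selected prescription".
- **Pill-count correction.** "we will change the daily dose of rivaroxaban assigned to 40 mg to 20 mg when the posology derived from dividing the quantity" by the interval between consecutive prescriptions (gap under 90 days) gives 20 mg. The stated reason is experience in Study 19330, where the instructions field for rivaroxaban "sometimes results in misclassifying as 40mg daily dose, usage that should be classified as 20mg daily dose according to pill count".
- **Apixaban class.** "Daily doses of 5mg will be considered as “reduced dose", with no reference to tablet strength.
- **Exclusion (section 9.2.3).** "Users of Apixaban apart from 5/10mg daily dose".
- **Analysis (section 9.7, item a).** Reduced-dose apixaban appears only as 2.5 mg twice daily, split by whether dose-reduction criteria are met, each part compared with warfarin.

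**The concern.** For apixaban, two different records give the same total: 5 mg once daily and 2.5 mg twice daily are both 5 mg/day. Classifying on the total alone cannot separate them. A text reading of 1 also overrides the twice-daily default, so nothing later in the written rules questions it.

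Inappropriate reduced-dose apixaban is the exposure behind the hypothesis in section 7, and describing its use is a secondary objective in section 8.2. If standard-dose users enter the cell, its frequency is overstated and its odds ratio moves towards that of standard-dose apixaban. The group they come from is several times larger than the cell, so a small error rate matters. Item 5.2 of the checklist in Annex 2 states that the validity of exposure measurement is not addressed, and section 9.9 does not list errors in reading dose text as a limitation.

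**Working it through.** **Step 1: trace of the rules**

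| Record | Posology used | Daily dose | Result |
|---|---|---|---|
| Apixaban 5 mg, text read as 1 | 1 | 5 mg | kept, reduced dose, no check |
| Apixaban 5 mg, text missing or unmapped | 2 | 10 mg | kept, standard dose |
| Apixaban 2.5 mg, text read as 1 | 1 | 2.5 mg | excluded |
| Apixaban 2.5 mg, text read as 2 | 2 | 5 mg | kept, reduced dose |
| Rivaroxaban 20 mg, text read as 2 | 2 | 40 mg | reset to 20 mg if pill count agrees |

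The first row lands in a 2.5 mg twice-daily cell of section 9.7: the inappropriate one if no reduction criteria are met, otherwise the appropriate one.

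**Step 2: the plan's own figures (section 9.5)**

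Inputs: at least 10,000 initiators per drug; annual rates of 1, 2 and 4%; 50% current users at index date; 30% of current apixaban users on reduced dose, half of them appropriately; two-sided 5%.

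- Events: 30,000 × 1% × 3 years = 900; likewise 1,800 and 3,600. Three years of mean follow-up is implied, not stated.
- Detectable odds ratios at 80% power, from a two-proportion comparison of exposure in cases and controls. The control-to-case ratio is not stated; 1:1 fits best. Inappropriate versus appropriate reduced apixaban: 3.54, 2.37, 1.82 (plan: 3.5, 2.4, 1.8). Inappropriate reduced apixaban versus warfarin: 2.20, 1.78, 1.52 (plan: 2.3, 1.8, 1.6 with at least 80% power).

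The plan's figures are reproduced closely enough to use its cell sizes.

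**Step 3: cell sizes**

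Current apixaban users: 10,000 × 50% = 5,000. Standard dose: 70% = 3,500. Reduced: 30% = 1,500. Inappropriate reduced: 750. The standard-dose group is 3,500 / 750 = 4.7 times the cell.

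**Step 4: contamination**

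Let q be the share of standard-dose users misread as once daily. The documents give no value, so a range is assumed. If all misread users lack reduction criteria, the spurious share of the cell is f = 0.70q / (0.15 + 0.70q).

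For ischaemic stroke, take a true odds ratio of 1.8 versus warfarin for the genuine cell and assume 1.0 for standard dose. The observed value is then (1 − f) × 1.8 + f.

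| q | Users added | f | Observed OR |
|---|---|---|---|
| 1% | 35 | 0.0070 / 0.157 = 4.5% | 1.76 |
| 3% | 105 | 0.0210 / 0.171 = 12.3% | 1.70 |
| 5% | 175 | 0.0350 / 0.185 = 18.9% | 1.65 |

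If only 85% of the misread users lack reduction criteria, f falls to 3.8% at q = 1% and 16.6% at q = 5%. If 2.5 mg tablets are misread at the same rate and excluded, the genuine cell shrinks to 750(1 − q), and the first-table shares become 35/777.5 = 4.5%, 105/832.5 = 12.6% and 175/887.5 = 19.7%. Neither variant changes the order of size.

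**Step 5: power for ischaemic stroke, inappropriate reduced apixaban versus warfarin**

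At 1:1 controls, power at a true odds ratio of 1.8 is 81.8% without misreading, 78.8% at q = 2% and 74.4% at q = 5%. With four controls per case it falls from 95.5% to 91.7% at q = 5%.

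**The case against.** The protocol documents no misreading of apixaban text. The one error it reports is rivaroxaban read too high, and the correction answers that observed error. Study 19330 also included 8,629 apixaban initiators, so the authors had a chance to see an apixaban problem. Section 9.1 says the algorithm is tuned by hand on recent prescription history, and section 9.2.1 mentions manual and free-text review. A 5 mg once-daily record among twice-daily ones could be noticed there. Some such records may be real, and for an under-dosing question a total of 5 mg/day is a defensible class. Pill count has limits too: a late refill looks like a lower posology, and the last prescription before the index date has no following interval, because only prior prescriptions count.

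Much of this stands. A reader might infer that the cell is in fact filled with misclassified users; without an apixaban error rate, the documents do not support that. A reader might also infer that the one-drug correction favours the sponsor's product. The stated reason is an error found in earlier work, so that does not follow. Nor should the 15 mg rivaroxaban tablet at two per day be added as a parallel fault: rules 3A and 3B assign that posology deliberately in defined situations.

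What does not stand is relying on the tuning. It is unspecified, while the written rules send these records into the cell. Even a genuine 5 mg once-daily record is not 2.5 mg twice daily, so the class and the label disagree whatever the error rate.

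**Conclusion.** The point holds as a gap in the algorithm and a mismatch between sections 9.3.1.1 and 9.7, not as a demonstrated bias. Apixaban read as once daily is unchecked: 5 mg tablets can join the reduced-dose cells while 2.5 mg tablets are dropped.

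The effect on the inappropriate cell is small at a 1% misread rate (4.5% of the cell, 1.8 observed as 1.76) and becomes material near 5% (about 19%, 1.8 observed as 1.65). These sizes rest on the section 9.5 split, on assumed misread rates, on all misread users lacking reduction criteria, and on standard-dose apixaban having an odds ratio of 1 versus warfarin. If that last value differs, the estimate is pulled towards it instead. The correction is worth making because it is cheap and the cell is central to the hypothesis.

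**What to change.** In section 9.3.1.1, before the dose exclusions of section 9.2.3 are applied:

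1. Extend the existing quantity/interval check (gap under 90 days; prior prescriptions only at index date) to apixaban 5 mg and 2.5 mg prescriptions read as once daily. Reset posology to 2 only when pill count supports it. Used in this one direction, a late refill leaves a record unrepaired but creates no new error.
2. Report the number of 5 mg once-daily records that remain. Keep them out of the 2.5 mg twice-daily cells, or show the results with and without them.
3. Reconcile the 5 mg/day class in section 9.3.1.1 with the cell labels in section 9.7, so that a record is assigned on strength together with posology.

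The cost is modest extra programming on fields already used for rivaroxaban, plus a small residual group outside the main cells.
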